GENERAL INFORMATION

Alerts with Risk Information to Increase Influenza Vaccinations

[name].
[contact]

March 13, 2023

IRB#: 2022-0502

BACKGROUND AND OBJECTIVES

On average, 8% of the US population gets sick from the flu each flu season (Tokars et al. 2018). Since 2010, the annual disease burden of influenza has included 9-45 million illnesses, 140,000-810,000 hospitalizations, and 12,000-61,000 deaths (CDC 2020). The CDC recommends a flu vaccination to everyone aged 6+ months, with rare exception; almost anyone can benefit from the vaccine, which can reduce illnesses, missed work, hospitalizations, and death (CDC 2019). Flu vaccination is especially important during the COVID-19 pandemic, to minimize flu/COVID-19 coinfections and conserve healthcare resources.

One barrier to vaccination is a lack of “cues to action,” and, in particular, the lack of direct recommendation from medical personnel (Schmid et al. 2017); this barrier is arguably the most effectively overcome by a simple nudge of clinicians, compared with barriers such as negative attitudes toward vaccination, low perceived utility of vaccination, and less experience with having received the vaccine. Nudges that increase clinician actions to recommend and order flu shots for their patients may therefore increase vaccinations more than attempts to nudge patients directly (e.g., by sending them text messages). Interruptive or “hard stop” alerts can help promote behavior that improves patient outcomes (Powers et al., 2018). And mechanisms that make an alert more salient can increase attention to a nudge and thus encourage action (Patel et al., 2017; Kim et al. 2017). These nudges are likely to be most effective when timely, for instance, as alerts to clinicians during those appointments (Milkman et al. 2021). In the 2020–21 flu season, Geisinger implemented a standard electronic health record (EHR) alert notifying clinicians when any outpatient they are seeing is eligible for a flu shot; yet, despite this alert, only a minority of patients are presently being vaccinated, especially at specialty appointments.

While most recover from influenza without treatment, the elderly, those with comorbidities, and other high-risk individuals can experience complications such as pneumonia, other respiratory illness, and death (Rothberg et al., 2008; Turner et al., 2003; WHO, 2010). Geisinger, a large health system in Pennsylvania, has partnered with Medial EarlySign (Medial; www.earlysign.com) to develop a machine learning (ML) algorithm to identify patients at risk for serious (moderate to severe) flu-associated complications based on existing EHR data. As part of our recent Roybal-funded pilots, Geisinger deployed this system during the 2020–21 and 2021–22 flu seasons and sent patients in the top 10% of predicted risk special messages (in addition to standard health system efforts) encouraging vaccination. Interim data from both pilots reveal that notifying patients about their high-risk status increases vaccination, but vaccination is not further increased by informing patients of how their risk was determined (Shermohammed et al., 2021) or by informing them of contributing risk factors from their medical records (Rosenbaum et al., 2021). Compared with patients, clinicians may be more receptive to information about individual patient risk factors, given their better understanding of medical diagnoses contributing to flu risk.

The present study will test the effectiveness of a clinician-facing nudge (e.g., salient, risk-based alert vs. a standard alert) on flu vaccination. This study builds on previous work supporting the effectiveness of salient alerts in encouraging flu vaccination (Kim et al., 2018; Patel et al., 2017) and extends it by focusing on alerts for people at high risk for flu and flu complications.

Specific Aims

Evaluate via randomized controlled trial the efficacy of a clinician-facing, EHR alert-based nudge promoting flu shots, alerting clinicians to their patients' high-risk status (with or without personalized contributing factors).

PROCEDURES

Research Design

Patients from the high-risk sample (primary target population) will be randomly assigned to one of at least two study arms. If necessary, we will randomize at the clinician or clinic level. Outcomes during the 2022–2023 flu season will be compared between study arms.

Study Population

1) Patients

Inclusion Criteria:

- Age 18+
- Have been determined to be in the top 20% of risk through Medial's ML algorithm
- Attend an appointment where the flu alert fires (Geisinger sets when flu alerts start and ends--between ~9/1/2022 and ~4/30/2023, as well as the trigger conditions for the alert, which includes valid departments and visits and excludes contraindications like Guillain-Barre syndrome)

2) Clinicians

Inclusion Criteria:

- Any Geisinger clinician who sees patient-participants in our study for an appointment where their flu shot alert fires

Recruitment and Enrollment

All patients will be recruited and enrolled from Geisinger; Massachusetts Institute of Technology (MIT)/National Bureau of Economic Research (NBER) collaborators will not be involved in recruitment or enrollment. Patients meeting the primary target population criteria will be enrolled into one of the experimental conditions. Anticipated enrollment number for this primary target population is 90,000. Only Geisinger clinicians for this primary target population will see the salient, risk-based alert for patients who were randomized to trigger it. Clinicians of patients who are not part of the study population will still see the standard flu alert if their patients are eligible for it as part of Geisinger's standard of care.

Detailed Study Procedures

Patients in the top 20% of risk for flu and flu complications based on the Medial EarlySign flu algomarker will be randomized to trigger a standard flu alert (specifically, a best practice alert) or a salient, specialized alert for clinicians throughout the 2022–23 flu season, stating the patients' level of risk (e.g., top 3%, top 10%, or top 20%). Among those who triggered the high-risk alert, we may further randomize this group to be shown or not shown the top factors contributing to patients' risk, based on Medial's algorithm. The high-risk alert will also include

text and color features to make the alert stand out among other alerts. Additionally, the high-risk alerts will be given priority, such that they are displayed above other unprioritized alerts (they will still show below high-priority alerts). The precise language and look of the alerts may change slightly from the attached drafts, as we are working with multiple teams at Geisinger, but the drafts are representative of the types of alerts that will be shown.

Geisinger introduces flu-related alerts on September 1st. As part of the research planning, randomization will occur in June 2022, in order to provide enough time to import risk scores and high-risk factors into Epic, so these data can be used to trigger the proper alerts. Because this intervention is timed to the 2022–23 flu season, the intervention period will begin ~9/1/22.

The primary outcome will be flu vaccination at the scheduled appointment, as recorded in the Geisinger EHR. We may limit the timeframe of the primary outcome to end earlier in the flu season (e.g., December), based on data suggesting that most patients get their flu shot by the end of the calendar year. If we choose this timeframe, we will still examine all data collected throughout the flu season. Additional outcomes to be measured between the patient's appointment and the end of the flu season will include: rates of flu diagnoses (both using the most rigorous biological tests, "high confidence flu", and using broader criteria that also include diagnosis codes and treatment information, "likely flu"), flu complications, and rates of other relevant healthcare utilization outcomes such as ER visits and hospitalizations. Finally, we will measure rates of COVID-19 vaccination in targeted patients.

Data Sources

All patients in this study will be in the top 20% of risk according to scores given by the Medial EarlySign flu algomarker. The development of this algorithm was already approved through a separate Geisinger IRB application (IRB number 2020-0211). Additionally, Geisinger deployed this system in a field study during the 2020–21 (IRB number 2020-0290) and 2021–22 flu seasons (IRB number 2021-0483) and contacted the identified patients with special messages (in addition to standard interventions conducted by the health system every flu season) to encourage vaccination.

In order to generate flu risk scores, Medial EarlySign has access to a de-identified, retrospective dataset in Geisinger's research environment. This environment is accessed by Medial EarlySign staff who have undergone appropriate training and are credentialed per Geisinger's research and Information Security/Access policies. This environment is protected by Geisinger Information Security Office standards that allow remote access to the Geisinger network in a 'sandbox'. All data and analysis are conducted within the secure environment and data do not leave the Geisinger network. The dataset contains EHR information on all patients who had a primary care encounter at Geisinger (outpatient or telemedicine) between 10/1/2008 and 4/13/2022.

Medial uses the retrospective dataset to generate flu risk scores for patients in that dataset who meet the following criteria:

1. Were born in the year 2004 or later (i.e., those turning 18 in the year 2022 and older)
2. Were alive according to the EHR as of April 2022 when the dataset was last updated
3. Either:
 - a. Currently have a Geisinger PCP assigned
 - b. Have been in the EHR since at least September 2021 AND have had at least one encounter in 2020–2022

After we obtain the base sample list from Medial, **Business Intelligence & Advanced Analytics** (BIAA), working with **Geisinger's Phenomics and Clinical Data Core** (PACDC), will pull a dataset to help us determine who meets our inclusion criteria and aid in NIH demographics reporting. This dataset will include demographic information, including patient birth date, race, ethnicity, and gender and/or sex. Finally, the dataset will include death date to ensure patients are living as of the date the data are extracted.

We will also obtain individual-level employee demographic information including age, gender, race, and ethnicity for provider-participants to aid in NIH demographics reporting. This information will be deidentified and aggregated prior to any external reporting or data sharing.

After the intervention is complete, we will obtain experimental outcome data for all population groups from BIAA & PACDC. This will include data on patient flu vaccination, diagnosis of flu, diagnosis of flu-like symptoms, presence of flu-associated complications, hospital visits, emergency department visits, and COVID-19 vaccination status. This dataset will additionally include patient characteristics that can serve as analysis covariates, such as: patient primary care provider and flu-related behavior and outcomes during previous flu seasons.

We may also request claims data from the Geisinger Health Plan (GHP; e.g., for claims related to flu vaccination, diagnosis, and complications). GHP claims data will be pulled by BIAA or the GHP data team (Pending approval from Research Contracts).

STUDY DATA DETAILS

Data Management Procedures and Confidentiality

The complete, identified study data will be accessed only by a Geisinger data broker and by limited Geisinger investigators with appropriate training and a legitimate need to know (i.e., Geisinger Co-Is and PIs), and any appropriately trained Geisinger staff, (e.g., clinicians, data analysts) who have a need to review the data for purposes of their normal Geisinger role.

A limited dataset containing dates of service and ZIP codes may be shared with any non-Geisinger collaborators (e.g., Additional Principal Investigator [name] and his team) under a Data Use Agreement (pending approval) in compliance with HIPAA's Privacy Rule and using data security protocols reviewed and approved by the Geisinger Security Office, Privacy Office, and Information Technology department.

All data will be electronic. Datasets with full identifying information will only be stored on Geisinger-managed, password-protected computers of the data brokers for the purpose of linking datasets from different sources.

Identifiable data gathered for this study will be retained for at least 3 years, as required by NIH policy, and will be deleted after 3 years or after analysis is complete. After the data have been fully analyzed, the deidentified dataset will be shared along with publications from this study. The deidentified data will not be destroyed or removed after any prespecified period of time has elapsed. We intend to permanently and securely archive the deidentified dataset at a research repository such as Open Science Framework (OSF) in order to be consistent with the best practices for open and reproducible science, as well as our obligation to the public as NIA-funded researchers.

All data analysis will be conducted by [name], [name], [name], or limited other Geisinger investigators with appropriate training, and our non-Geisinger Collaborators. We

will analyze the data using standard behavioral research analysis methods, including computing bivariate correlations, using generalized linear models, using non-parametric models for non-normally distributed data, and entering variables as independent predictors in regression models to attempt to predict desired outcomes.

RESEARCH ACTIVITIES AT OTHER SITES

Geisinger is the lead research team for this multi-site study. Massachusetts Institute of Technology (MIT) and National Bureau of Economic Research (NBER) study personnel are considered not considered engaged in human subject research. Research activities conducted at MIT and NBER will be limited to data analysis, using limited data, as described above. MIT and NBER will not be involved in study recruitment/enrollment or intervention administration.

References

Centers for Disease Control and Prevention. (2019). Who needs a flu vaccine and when. <https://www.cdc.gov/flu/prevent/vaccinations.htm> (Oct 11).

Centers for Disease Control and Prevention. (2020). Disease Burden of Influenza. <https://www.cdc.gov/flu/about/burden/index.html> (Jan 10).

Kim, R. H., Day, S. C., Small, D. S., Snider, C. K., Rareshide, C., & Patel, M. S. (2018). Variations in influenza vaccination by clinic appointment time and an active choice intervention in the electronic health record to increase influenza vaccination. *JAMA network open*, 1(5), e181770. <https://doi.org/10.1001/jamanetworkopen.2018.1770>

## Scientific Background and Objectives

The CDC (Centers for Disease Control) recommends a flu vaccination to everyone aged 6+ months, with rare exception; almost anyone can benefit from the vaccine, which can reduce illnesses, missed work, hospitalizations, and death. One barrier to vaccination is a lack of "cues to action," and, in particular, the lack of direct recommendation from medical personnel; this barrier is arguably most effectively overcome by a simple nudge of clinicians, compared with barriers such as negative attitudes toward vaccination, low perceived utility of vaccination, and less experience with having received the vaccine.

Geisinger partnered with Medial EarlySign (Medial) to develop a machine learning (ML) algorithm to help identify people at risk for serious flu-associated complications based on existing electronic health record data. Eligible at-risk patients were randomized to an active control group (clinician is shown a standard flu alert) or one of two experimental groups (clinician is shown an alert indicating patient's high risk, with or without describing the patient's factors contributing to that risk).

## Methods

Patients in the top 20% of risk for flu and complications, according to Medial's algorithm, were pre-randomized into the following arms:

1. Standard Alert: For flu-shot best-practice alert (BPA)-triggering appointments, the standard flu-shot BPA fires.
2. High-risk Alert: For BPA-triggering appointments, a modified BPA fires. This BPA includes salient features (e.g. larger alert headers, bold face, red font), and alerts the clinician that the patient is at high risk for flu and its complications.
3. High-risk Alert with Risk Factors: For BPA-triggering appointments, a modified BPA fires. This BPA includes salient features (e.g. larger alert headers, bold face, red font), and alerts the clinician that the patient is at high risk for flu and its complications. This BPA also presents the top factors contributing to the patient's high risk.

Patients are subsequently enrolled in the study if they attend at least one appointment where their assigned flu-shot BPA fired.

Clinicians are enrolled if they see a flu-shot BPA for an enrolled patient at a qualifying appointment.

## Power Analysis

We expect at least 60,000 patients to be enrolled (at least 20,000 per arm). With this sample size, we will have 80% power to detect an increase in flu vaccination rates from 35% to 36.34% with two-tailed alpha = .05 for any comparison between arms.

## Planned Analyses

**Primary Outcome:** Patient received a flu vaccine (yes/no) [Time Frame: At the 1 day visit]

**Question 1:** Do salient alerts indicating that patients are at high risk for flu and flu-related complications increase the likelihood that the patients will get vaccinated?

**Analysis 1 (Confirmatory):** We will test the hypothesis that patients whose clinicians were shown alerts with information about their risk status (patients randomized to the High-risk Alert or High-risk Alert with Risk Factors arms) will exhibit improved flu vaccination rates compared with patients in the Standard Alert arm.

For this analysis, we will run an OLS regression, including a binary predictor variable coding separately for baseline and the two High-risk Alert arms.

**Question 2:** Do alerts with information about a patient's factors that contribute to their high risk of flu and flu-related complications increase the likelihood that the patients will get vaccinated?

**Analysis 2 (Exploratory):** We hypothesize that patients whose providers were shown alerts with the factors that contributed to a patient's high risk (High-risk Alert with Risk Factors arm) will exhibit improved flu vaccination rates compared with patients in the arm with no risk factors (High-risk Alert arm).

For this analysis, we will run an OLS regression, including a binary predictor variable coding separately for each of the two High-risk Alert arms.

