## Analysis Notes

Analyses of the primary outcome will be limited to the first in-person appointment for each patient enrolled in the study. We will run a sensitivity analysis that includes patients who only attend telehealth appointments during the study.

Recent work suggests that OLS regressions are appropriate in randomized experiments with binary outcome variables such as ours (Gomila, 2021).

As the treatment variation is at the individual level, we will report heteroskedasticity-robust standard errors. We will also explore the impact of clustering these standard errors at the clinic and clinic-date levels to allow for dependence across observations within these clusters. We will also investigate heterogeneity across clinics that vary along characteristics of interest, including prior-year vaccination rates.

We may run additional robustness checks. These checks may include focusing on additional inclusion/exclusion criteria (e.g., including subsequent visits with alerts for a given patient) and subpopulations (e.g., different visit types).

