## **Additional Exploratory Analyses**

### **1. Age and sex**

While older patients tend to be aware of their increased vulnerability, younger patients may be more surprised to learn of their high-risk status. Additionally, our previous work suggests that males and females are differentially likely to get vaccinated as a function of age, with younger females *more* likely to get vaccinated than males, and older females *less* likely to get vaccinated than older males.

To test the relation between flu shots, age and sex, we will run an OLS regression including binned patient age (18–24, 25–34, 35–44, 45–54, 65+), sex, and their interaction.

Additionally, we will test for an interaction between age, sex, and study arm, as people of different ages and sexes may be differentially receptive to different alert versions.

We may also test whether alert effectiveness varies by clinician age and/or sex.

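### Analyses 1 and 2 adjust for no baseline covariates, although prior-season flu behavior, risk score, age and sex are due to be available: a cheap precision gain is left unused

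*SAP*

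**What the plan says.** Analysis 1 in the SAP's Planned Analyses compares the two high-risk alert arms together with the standard alert: "we will run an OLS regression, including a binary predictor variable coding separately for baseline and the two High-risk Alert arms". Analysis 2 compares the two high-risk arms with each other: "we will run an OLS regression, including a binary predictor variable coding separately for each of the two High-risk Alert arms". The SAP's Analysis Notes add heteroskedasticity-robust standard errors, exploratory clustering and heterogeneity across clinics. They add no patient-level covariate.

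The data for adjustment are planned for or already held:

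- The protocol's Data Sources section says the outcome dataset will hold "patient characteristics that can serve as analysis covariates, such as: patient primary care provider and flu-related behavior and outcomes during previous flu seasons".
- Risk scores exist around the time of randomization. Under Detailed Study Procedures, "randomization will occur in June 2022, in order to provide enough time to import risk scores and high-risk factors into Epic".
- On the eligibility extract, Data Sources says: "This dataset will include demographic information, including patient birth date, race, ethnicity, and gender and/or sex".

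The SAP uses age, sex and risk level only in its Additional Exploratory Analyses, and uses no patient-level flu history anywhere. The nearest item is clinic-level prior-year vaccination, as a source of heterogeneity.

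**The concern.** In a randomized comparison analyzed by linear regression with robust standard errors, adding variables fixed before randomization leaves the target, a difference in vaccination rates, unchanged. It removes the part of the outcome variance that those variables explain. Previous vaccination is a natural candidate: the background sections of both documents list little experience with the vaccine as a barrier, and the SAP reports that vaccination varies jointly with age and sex.

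Two things are at stake. The first is precision, which matters most for Analysis 2 and for effects below the design difference of 1.34 points. Precision also carries over to later analyses, because the SAP runs its other pre-specified outcomes only where flu vaccination differs significantly. The second is pre-specification. The protocol describes characteristics that can serve as covariates but nobody has listed them, so an adjusted estimate presented later could not be shown to have been planned.

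**Working it through.** **Inputs.** From the SAP's Power Analysis: control rate 35%, comparison rate 36.34%, two-sided alpha 0.05, 20,000 per arm. Analysis 1 pools two arms, so it compares 40,000 with 20,000. The protocol's enrollment figure is larger: "Anticipated enrollment number for this primary target population is 90,000", or 30,000 per arm if split equally. R² is not given and is assumed.

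**The plan's own figure.** With SE = √[p₁(1−p₁)/n₁ + p₂(1−p₂)/n₂] and power = Φ(difference/SE − 1.96):

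- Pairwise: SE = √[(0.35×0.65 + 0.3634×0.6366)/20,000] = 0.479 points. Power = Φ(1.34/0.479 − 1.96) = 79.9%, which reproduces the stated 80%.
- Pooled: SE = √[0.35×0.65/20,000 + 0.3634×0.6366/40,000] = 0.414 points. Power = 89.9%.

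The detectable difference at 80% power is (1.96 + 0.84) × SE: 1.34 points pairwise and 1.16 points pooled.

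**Assumed R².** Suppose half of the patients were vaccinated last season and the overall rate is 35%. Then R² = 0.25 × gap² / (0.35 × 0.65), where the gap is the difference in this season's rate between previous vaccinees and others. Gaps of 20 points (45% vs 25%), 30 points (50% vs 20%) and 40 points (55% vs 15%) give R² of 0.044, 0.099 and 0.176. A low case of 0.02 is added.

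**Effect of adjustment.** The SE is multiplied by √(1−R²), which is equivalent to 1/(1−R²) − 1 more patients.

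| Assumed R² | SE factor | Equivalent extra patients | Pooled: detectable difference | Pooled: power at 1.34 points | Pooled: power at 1.0 point | Analysis 2: detectable difference | Analysis 2: power at 1.34 points |
|---|---|---|---|---|---|---|---|
| none | 1.000 | – | 1.160 | 89.9% | 67.6% | 1.342 | 79.9% |
| 0.02 | 0.990 | 2% | 1.148 | 90.5% | 68.5% | 1.328 | 80.7% |
| 0.044 | 0.978 | 5% | 1.134 | 91.1% | 69.5% | 1.312 | 81.6% |
| 0.099 | 0.949 | 11% | 1.101 | 92.6% | 72.1% | 1.274 | 83.8% |
| 0.176 | 0.908 | 21% | 1.053 | 94.6% | 75.8% | 1.218 | 86.9% |

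At 30,000 per arm the unadjusted detectable differences are 0.95 points (pooled) and 1.10 points (pairwise), and the same percentage reductions apply.

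**Simulation check.** Over 200 simulated trials of 60,000 with no effect and robust standard errors, the mean ratios of adjusted to unadjusted SE were 0.978, 0.949 and 0.908 for the three vaccination-history scenarios, as the formula predicts.

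**The case against.** The strongest reply is that nothing here is broken. An arm-only regression with robust standard errors is unbiased, transparent and delivers the promised power. The confirmatory contrast has about 90% power at the design difference with 60,000 patients, and 97.7% with 90,000. This stands, and it is why the point concerns efficiency only.

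The gain also rests wholly on assumed R². A 50% prevalence of previous vaccination is the value that maximizes R² for a given gap. A gap of 10 points gives R² of only about 0.011, and at R² = 0.01 pooled power at 1.34 points moves from 89.9% to 90.2%. The outcome is vaccination at one alert visit among patients still eligible for a shot, which may weaken the association. The risk score has a restricted range, since everyone is in the top 20%. The protocol speaks of flu-related behavior without naming vaccination. All of this stands as a limit on the size of the gain.

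On pre-specification, the SAP can be read as already fixing the unadjusted estimate. That is fair, but the wording does not exclude further terms, and the protocol's general analysis paragraph allows predictors to be entered without listing any.

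Finally, with 2:1 pooling, additive adjustment is not guaranteed to reduce variance when covariate effects differ by arm. This has little practical force here: with an assumed gap of 30 points in the control arm and 33 in the alert arms, the simulated SE ratio was 0.946.

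**Conclusion.** The concern holds as an unused improvement that should be taken up; it is not a validity error. Under assumed R² of 2% to 17.6%, adjustment shortens confidence intervals by 1% to 9%, worth about 2% to 21% more patients. Power at 1.34 points rises by about 1 to 7 points in Analysis 2 and by about 0.6 to 5 points in the pooled contrast. If R² is 2% or less, the precision gain is negligible and the main benefit is a fixed covariate list. Confidence in the size is moderate at best, because it depends on how well previous vaccination predicts vaccination at the index visit, which neither document reports.

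The argument that the covariates precede randomization relies on the protocol's date of June 2022. The SAP's Project Status section says summer 2023, which cannot fit its own study end of 4/1/23 and should be corrected.

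**What to change.** Before outcome data are seen, amend Analyses 1 and 2 to include a fixed list of pre-randomization covariates:

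- flu vaccination in the previous season (yes, no, unknown), measured before the 2022–23 season;
- risk-score band (top 3%, 10%, 20%);
- age and sex. Use age bands that cover all ages, because the exploratory model's "binned patient age (18–24, 25–34, 35–44, 45–54, 65+), sex, and their interaction" omits 55–64. An age-by-sex term would match the pattern the SAP itself describes.

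Keep the robust standard errors, state which estimate is primary, and report the unadjusted one alongside. The unknown category deals with missing vaccination history.

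Leave department and month of the index visit out of the primary model. Both are determined after randomization. The SAP's Analysis Notes say "Analyses of the primary outcome will be limited to the first in-person appointment for each patient enrolled in the study", so an assigned alert at an earlier telehealth visit could precede that appointment.

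The cost is SAP wording. Risk score, birth date and sex are already obtained. The data request should be checked to confirm that it includes previous-season vaccination. The documents do not show whether outcomes were still unseen when the SAP was finalized; if they had been seen, the adjusted analysis should be labeled as added afterward.
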